# Weight Decrease or Appetite Decrease

The study staff will take precautions against the possibility of weight loss and/or decreased appetite by monitoring weight at each study visit. If there is a notable decrease in weight or appetite, the study staff will refer the subject to a licensed dietician or gastrointestinal specialist. If it is determined that the weight loss is related to the study drug the LPI may decide to decrease the dose of study drug. This will be determined on a case to case basis.

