# The inclusion criteria for enrollment in this study include:

- Subject is male or non-pregnant, non-lactating female, age 4 to 25 years, inclusive as of the day of the screening visit. Female subjects of childbearing potential must have a negative serum pregnancy test at screening. Subjects of childbearing or child-fathering potential must be willing to use medically acceptable forms of birth control, which includes abstinence, while in this study and for 90 days after the last dose of study drug.
- Subjects must have a diagnosis of Sunflower Syndrome, where seizures are not completely controlled by their current treatment plan.

- Subjects must experience seizures including absence seizures and/or generalized tonic-clonic seizures which involve seeking out a light source, staring at the light source, and waving one hand in front of their eye(s). Subject's must experience an average of 6 handwaving associated with absence seizures and/or generalized tonic-clonic seizures per week.
- Evidence of EEG in the medical history that shows generalized spike and wave discharges between seizures and a strong photoparoxysmal response during photic stimulation. Acceptable evidence includes a copy of the EEG trace, EEG report, or physician note that appropriately describes the EEG findings.
- All medications or interventions for epilepsy must be stable for at least 4 weeks prior to screening and are expected to remain stable until Month 3.
- Subject and/or parent/guardian has been informed of the nature of the study and informed consent has been obtained from the subject and/or legally responsible parent/guardian.
- Subject has provided assent in accordance with Institutional Review Board (IRB)/Ethics Committee requirements, if capable.
- Subjects parent/caregiver is willing and able to be compliant with diary completion, visit schedule, and study drug accountability.

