# **V. STUDY PROCEDURES**

The investigational drug to be used in this study is fenfluramine hydrochloride (ZX008) manufactured by Zogenix, Inc..

ZX008 will be supplied as an oral solution in a concentration of 2.5 mg/mL. The subjects will be treated on an outpatient basis and will not require hospital admission. ZX008 will be administered on a twice daily basis.

The study will initially consist of a 4 week baseline period, during which handwaving associated with absence seizures and/or generalized tonic-clonic seizures will be recorded in a seizure diary on a daily basis. Subjects will meet enrollment criteria if they have an average of 6 generalized tonic-clonic and/or handwaving associated absence seizure per week.

If enrollment criteria is met, the subject will enter a titration period. The starting dose will be 0.2 mg/kg/day for the first 14 days. The dose will be increased every 2 weeks as tolerated by 0.2 mg/kg/day, to a maximum dose of 0.8 mg/kg/day, or a total maximum dose of 30 mg/day. The subject will remain on 0.8 mg/kg/day, 30 mg/day, or maximum tolerated dose for a 6 week maintenance period.

Site personnel will call the subject and/or their parent/caregiver every 11-14 days during the titration period before their next scheduled dose increase.

There will be 5 study visits within a 6 month period. After Visit 5, visits will occur every 6 months for an assessment in the clinic for subjects who respond to treatment with at least a 30% reduction in seizure frequency.

Seizure frequency will be tracked with the use of a daily seizure log. In the event that seizure frequency is markedly reduced compared to baseline after starting the study drug the LPI will discuss with the subject and/or their caregiver about adjusting the dose of concomitant seizure medications. If seizure frequency is markedly increased compared to baseline after discontinuing other medications which were taken as standard of care the LPI may decide to adjust dose of other seizure medications or reintroduce the medications that were taken as

IND Visit Schedule					
Visit Number	Visit Type	Time Point			
1	Baseline	Day -28			
2	Titration	Day 1 (+14 days)			
3	Titration and/or	28 days from Visit 2			
	Maintenance	(±7 days)			
4	Maintenance	56 days from Visit 2			
		(±14 days)			
5	Maintenance	84 days from Visit 2			
		(±14 days)			
Continuous	Maintenance	Each 6 Months			
		following Visit 5			
		(±14 days)			

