#### At Visit 1, 2, 3, 4, 5, (Day -28, Day 1, Day 28, Day 56, Day 84) and All Sequential Visits

For the period during which COVID-19 contingency plans are in place at Partners/MGH, all study visits, including the Screening Visit, will be conducted as telemedicine appointments through a PHS IS-approved Zoom software. A weblink will be provided to subjects ahead of each appointment.

For study visits conducted as telemedicine appointments, required study procedures will be performed at sites local to the subject. We will provide each subject with location and scheduling information for their respective local site. The required study procedures that will be performed locally are:

- Echocardiograms (Visits 1, 5 and Extension Visits 1 and 2)
- Labs (CBC, CMP, AED) (as required by Principal Investigator)

Echocardiograms, and labs (CBC, CMP, AED) conducted locally will be sent to the Principal Investigator to ensure patient safety, and, in the case of ECHOs returning positive results, will be sent to a central reader, BioMedical Systems, Inc. (BMS).

These visits will take about 2 hours. During these visits, the following will be conducted:

- All the study eligibility criteria will be reviewed to confirm that the subject is still eligible.
- The subjects past and current medical, neurological, and epilepsy history will be reviewed at Visit 1 only.
- The study doctor will review the subject's current epilepsy status from the previous visit including: the amount of seizures they had, the types of seizures they experienced, and the duration of each of their seizure types.
- The subject will be asked about their health and the medicines that they have taken or are currently taking.
- Perform a physical and neurological exam. These exams are a series of simple questions and tests that provide very important information about the subject's systems. During the neurological exam, the treatment doctor will ask the subject to stand straight and walk, see how well the subject can move during the visit, and talk to the subject to see how they are doing. The treatment doctor will also look at the subject's eyes and see how their face, arms, and legs feel when touched.
- Vital signs including: blood pressure, heart rate, respiratory rate, along with height, and weight will be measured.

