# Safety Telephone Calls (Day 14, Day 42, Day 70)

At times during the study, the site personnel will call the subject and/or their parent/caregiver to see if they are adjusting well and whether they are having any difficulties on the medication. The subject will be

contacted by the study team by telephone at day 14, day 42, and day 70after the start of study drug and the following will be discussed:

- 1. Review of any current adverse events and/or adverse events of special interest that the subject has experienced.
- 2. Review of all medicines the subject is currently taking.

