# Table 1. Clinical Measures Enacted Upon Increasing Severity ofECHO Findings

	Valve			
Severity	Aortic	Mitral	Pulmonary	Tricuspid
Trace (≤18 years)	Level 2	Level 2	Level 1	Level 1
Trace (>18 years)	Level 1	Level 1	Level 1	Level 1
Mild (≤18 years)	Level 2	Level 2	Level 1	Level 1
Mild (>18 years)	Level 2	Level 1	Level 1	Level 1
Moderate	Level 3	Level 3	Level 3	Level 3
Severe	Level 3	Level 3	Level 3	Level 3

Level 1: Continue per protocol

Level 2:

- 1. If there is a desire to continue study medication:
  - a. The principal investigator will evaluate the efficacy to date based on study diaries and consult with the parent/guardian, and determine whether study treatment was associated with significant, meaningful benefit in number, severity and/or duration of seizures and/or on the impact on daily functioning.
  - b. The principal investigator will consider whether the subject has had reasonable trials (dose and duration) of other available anticonvulsants, alone or in combination, and not maintained the level of seizure control currently achieved with study medication.
- 2. If the principal investigator feels consideration of continued treatment is warranted considering benefit and potential risk, and the parent/guardian feels strongly that the child be maintained on the study medication when understanding the risks, the parent/guardian must sign a statement acknowledging their understanding of the positive findings and possible risks associated with continuing in the study. The child should provide assent if appropriate. If both of these conditions are not met, the subject is discontinued from treatment.
- 3. The principal investigator prepares a case history and rationale for continuation to review with the local cardiologist, including consideration of effects on seizures and comorbidities.
- 4. The principal investigator and local cardiologist will make a determination of appropriate path, including the possible outcomes:
  - a. Discontinue study medication
  - b. Increase frequency of ECHO and ECG monitoring
  - c. Add additional ECG and/or ECHO measures to be monitored
  - d. Reduce the dose of study medication

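### The weight rule acts only on a decrease, so a growing child whose weight stalls without a noticed appetite fall does not trigger it

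*Protocol*

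**What the plan says.** Section VII of the protocol, under Weight Decrease or Appetite Decrease, has staff follow weight at every study visit and then sets two actions.

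- Referral, which is mandatory: "If there is a notable decrease in weight or appetite, the study staff will refer the subject to a licensed dietician or gastrointestinal specialist".
- Dose reduction, which is discretionary: "If it is determined that the weight loss is related to the study drug the LPI may decide to decrease the dose".

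The section does not mention height, BMI, growth or expected gain. It applies to everyone admitted under the age criterion in section III: "Subject is male or non-pregnant, non-lactating female, age 4 to 25 years, inclusive as of the day of the screening visit".

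Section V places Visit 5 at 84 days from Visit 2 and then continues: "After Visit 5, visits will occur every 6 months for an assessment in the clinic for subjects who respond to treatment". Response means a seizure reduction of at least 30%, and no end to this phase is given. The visit procedures do collect the data a growth check would need: "Vital signs including: blood pressure, heart rate, respiratory rate, along with height, and weight will be measured". No rule uses them in that way.

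**The concern.** In an adult, weight loss is the natural sign of a drug that suppresses appetite. In a child who should be gaining weight, poor intake can show first as slow gain. That child falls behind while the recorded weight stays level or even rises, so a trigger defined as a decrease does not fire.

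The risk is one the protocol itself names. Section VII, In Human Trials, lists anorexia and decreased appetite from the Dravet syndrome studies, and weight loss from the trials in children and adolescents with autism or ADHD. The weight and appetite section is the stated precaution. For a stalled child, its weight criterion is silent, and detection depends on someone noticing a change in appetite or on general safety review. The mandatory step that is missed is the referral, since dose reduction is optional for every subject. The efficacy analysis is not touched.

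**Working it through.** **Step 1: the triggers against a stalled child.** The protocol states no figure to reproduce, so the first check is on the text.

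| Action | Condition in section VII | Child with flat or slow-rising weight, no appetite fall noticed |
|---|---|---|
| Referral (required) | notable decrease in weight or in appetite | not met: weight change is zero or positive |
| Dose reduction (optional) | drug-related weight loss | not met: there is no loss |

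The word notable is left to judgement, but no choice of threshold helps. The condition points in the wrong direction for this child.

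**Step 2: the rest of the protocol.** Adverse events are reviewed at each visit and at the safety calls on days 14, 42 and 70, where the item is "Review of any current adverse events and/or adverse events of special interest that the subject has experienced". Section IX has the investigator and nurses review safety data, and it allows withdrawal for an adverse event or on the investigator's opinion. The Virtual Visits section adds contacts between clinic visits in the extension; after a year these are held only as the investigator sees fit. All of these permit action. None asks anyone to set weight against expected growth.

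**Step 3: when the gap matters.** The growth inputs are assumptions, because the documents give none. For a young school-age child:

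- expected gain g = 2 to 3 kg a year (mid-range 2.5);
- weight-for-age standard deviation s = 3 to 5 kg (mid-range 4).

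Gain is treated as linear and s as constant. Times come from the visit schedule, counted from Visit 2: Visit 5 at day 84, then extension visits at about 84 + 182 = 266, 84 + 365 = 449 and 84 + 548 = 632. With a year of 365.25 days, the first three are t = 0.230, 0.728 and 1.229 years.

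For a full stall, the shortfall in kg is g × t and the shortfall in SD is g × t / s. At mid-range:

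- day 84: 2.5 × 0.230 = 0.57 kg; 0.57 / 4 = 0.14 SD;
- day 266: 2.5 × 0.728 = 1.82 kg; 1.82 / 4 = 0.46 SD;
- day 449: 2.5 × 1.229 = 3.07 kg; 3.07 / 4 = 0.77 SD.

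The range takes g = 2 with s = 5 at the low end and g = 3 with s = 3 at the high end. At half the expected gain, every shortfall is halved.

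| Day | Full stall, SD (range) | Half the expected gain, SD (range) | Raw weight change |
|---|---|---|---|
| 84 | 0.14 (0.09 to 0.23) | 0.07 (0.05 to 0.11) | zero, or a gain |
| 266 | 0.46 (0.29 to 0.73) | 0.23 (0.15 to 0.36) | zero, or a gain |
| 449 | 0.77 (0.49 to 1.23) | 0.38 (0.25 to 0.61) | zero, or a gain |

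**Step 4: time to a shortfall of 0.5 SD**, used here only as a benchmark: t = 0.5 × s / g.

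- Full stall: 0.5 × 4 / 2.5 = 0.80 years, about day 292. Fastest: 0.5 × 3 / 3 = 0.50 years, day 183. Slowest: 0.5 × 5 / 2 = 1.25 years, day 457.
- Half the expected gain: twice as long, 1.6 years, about day 584 (365 to 913).

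In the mid-range cases the benchmark would first be visible at the second extension visit (day 449) and the third (day 632). The weight criterion is not met at any of these times.

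**The case against.** The best answer is that the protocol as a whole does not leave the child unwatched. Height, weight and a physical examination are scheduled at each visit, adverse events are reviewed repeatedly, the extension has virtual visits as well as clinic visits, and nothing forbids referral or dose reduction outside this section. Slow gain could itself be recorded as an adverse event. This stands, and it is why the point is minor. It does not supply the missing prompt: a reader who follows the weight rule as written has no reason to plot a weight that has not fallen.

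Second, the referral rule has an appetite criterion, the named drug effects act through appetite, and a reliable caregiver is an entry requirement. Many affected children would therefore be caught. This also stands. What remains is the child whose intake falls gradually without anyone remarking on it. How often that happens is not known.

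Third, a clinician might read a decrease in weight as a fall in weight-for-age. That would be sensible, but the text does not say it, and the companion sentence speaks plainly of weight loss.

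Fourth, the growth figures come from outside the document. They are assumptions, and they only show when a stall would become visible; they do not predict that one will occur.

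The protocol does grade its other monitored risk by age: Table 1 separates subjects of 18 years and under from older ones for trace and mild valve findings. That concerns valve grading and not growth, so it shows only that action levels by age were thought workable here. It does not create a contradiction.

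**Conclusion.** The concern holds for the weight and appetite section read on its own. Both actions require a decrease, so a child who stalls or gains too slowly, with no appetite fall noticed, meets neither at any threshold. The effect is negligible in the 84-day core period and builds in the open-ended extension: under the assumed growth figures, a full stall reaches about 0.77 SD at day 449 (0.49 to 1.23). The number of subjects still growing among the planned maximum of 20 is unknown, as is the frequency of a stall without an appetite change. Severity is minor, with medium confidence. No endpoint or efficacy conclusion depends on it.

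**What to change.** Make two short changes in section VII. Extend the referral condition with *or inadequate weight gain for age*, and let the optional dose reduction apply to drug-related *weight loss or inadequate weight gain for age*. For subjects still growing, convert the heights and weights already scheduled to weight-for-age and BMI-for-age z-scores on a growth reference, and review the change from baseline at each visit. The threshold and the choice of action can stay with the investigator, as they do now.

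The cost is a chart conversion and a few more children flagged for review. Telemedicine visits need one addition. The list introduced by "The required study procedures that will be performed locally are" contains only echocardiograms and laboratory tests, so a height and weight reading would have to be arranged for those visits. The existing promise to follow weight at every visit already requires the weight.

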# Additional Risk

The subject taking part in this treatment involves some risks and possible discomfort as noted below:

- If the treatment does not work for the subject, the subject may see no change or an increase in their seizures. If there is an increase in seizure frequency the LPI may decide to lower the dose of the study drug or other seizure medications.
- The treatment drug may cause unpleasant side effects or reactions, as described below.
- Since ZX008 is investigational, there may be risks and side effects that are unknown. Any drug has a possible risk of an allergic reaction.

# ZX008 (Fenfluramine Hydrochloride)

# Animal Models:

Fenfluramine has been studied in young rats. In those studies, fenfluramine was given in doses similar to those the subject may receive and was shown to reduce activity and to induce learning and memory deficits. Fenfluramine was also shown to reduce certain chemicals in the brain, including serotonin, but the long-term effects of this are not known.

The relevance of the animal data to humans is not known. Not many learning and memory studies have been conducted with fenfluramine in humans. Of those that are published, the results are variable with some studies reporting no effect while other studies report some decrements or some improvements. Two studies have been conducted in children. Children were dosed daily for four weeks in one study and for four months in the other study. At the highest dose, which was 1.5 mg/kg/day in both studies, no adverse effects of fenfluramine were found on learning and memory tasks in either study.

# In Human Trials:

The possible side effects of fenfluramine (as observed in 3 open-label studies involving pediatric and young adult populations with Dravet Syndrome at doses of up to 30 mg/ day) were:

• Somnolence (sleepiness/ drowsiness)

- Anorexia
- Status Epilepticus (a seizure lasting more than five minutes or when seizures occur close together and the person is not able to recover in between seizures for more than five minutes)
- Decreased appetite
- Abnormal behavior
- Mild heart valve thickening without clinical significance
- Seizures/Seizure cluster (seizure clusters are when seizures occur in groups over several hours or days)
- Vomiting

In addition, fenfluramine has been studied in 13 clinical trials in an obese adult population at doses of 60-120 mg/day. The commonly reported adverse events from these trials were:

# Most Common Adverse Events (15-16% of study subjects had these symptoms):

- Diarrhea
- Drowsiness

Less Frequent Adverse Events (2-7% of study subjects):

- Dizziness
- Elevated mood
- Frequent urination
- Headache
- Insomnia
- Tiredness

Fenfluramine has also been studied in small trials in children and adolescents with autism and/or ADHD (attention deficit hyperactivity disorder). The commonly reported adverse events from these trials were:

- Drowsiness
- Increased withdrawal symptoms
- Irritability
- Lack of energy
- Sleeplessness (insomnia)
- Weight Loss

#### Risks from the study procedures:

- **Blood Sample Collection**: Taking blood from the subject's arm may sometimes cause pain/discomfort at the site where the blood is drawn, bruising, bleeding, occasional lightheadedness, redness, and/or swelling, and, rarely, feeling faint or infection.
- **EEG (electroencephalogram)**: Skin irritation is rare but could occur during or after an EEG from the sensors, gel, or glue that is used.
- ECHO (echocardiogram): An ECHO is a test that uses sound waves to examine the subject's heart. A technician will place sensors on the subject's chest that are connected by wires to a machine and the technician will then move a wand over their chest. The wand may have a small amount of cool gel on the end to make it move more easily. The subject may feel some pressure on the chest during this procedure. If they need to receive a sedative because they are unable to stay still for this procedure, the subject may experience extra sleepiness, slow or difficult breathing, a drop in blood pressure, feeling sick to their stomach, vomiting (throwing up), restlessness, or not knowing where they are when they wake up.
- **Questionnaires**: A questionnaire may contain questions that are sensitive in nature. The subject and/or their caregiver/parent may refuse to answer any question that makes them feel uncomfortable. If the subject has concerns after completing the questionnaire, they should talk to their study doctor.
- **Reproductive risks**: The subject should not become pregnant or father a baby while on this study because it is not known whether the drugs in this study can affect an unborn baby. Females should not breastfeed a baby while on this study. It is important to understand that if the subject is able to become pregnant or father a baby they need to use birth control while on this study. The subject should check with their study doctor about what kind of birth control methods to use and how long to use them. Some methods might not be approved for use in this study. If the subject is capable of having a baby, their blood will be tested to confirm that they are not pregnant.
- **Unknown Risks**: The experimental treatment may have side effects that no one knows about yet. The study staff will let the subject know if they learn anything that might make the subject change their mind about participating in the study.

As with all studies, there is a potential to breach confidentiality. Assigning a study number and keeping the log in a safe physical or electronic place will reduce the risk. Additionally, if the study treatment does not work for the subject, they may see no change or an increase in their seizures. ZX008 may cause unpleasant side effects or reactions. Since ZX008 is an investigational medication, there may be risks and side effects that are unknown.

